15.2.2.6. University of Pennsylvania Smell Identification Test (UPSIT™)

The UPSIT™ is composed of 40 odorants embedded on scent strips that are released when scratched with a sharply tipped object (Doty, Shaman, & Dann, 1984). The UPSIT™ is comprised of 4 booklets, each containing 10 microencapsulated (scratch & sniff) odours. The UPSIT™ is a forced-choice test, and subjects will be instructed to identify each odorant with alternatives accompanying each test item. The total olfaction score using the UPSIT™ is defined as the number of odorants correctly identified out of the 40 odours tested, with higher scores designating better olfactory performance.

The total olfaction score will be collected on the UPSIT eCRF page. The change from baseline in UPSIT™ total score will be calculated at each post-baseline visit as per Section 6.7.

15.2.3. MISSING DATA IMPUTATION METHODS FOR SECONDARY EFFICACY ENDPOINTS

15.2.3.1. Missing Data Imputation Methods for Key Secondary Efficacy Endpoints

For the primary analysis of the CFBL in CS7DA4S score at Week 24 key secondary efficacy endpoint, LOCF and multiple imputation will also be used to impute missing data for sensitivity analyses (refer to Section 15.1.4).

For bilateral Zinreich score and time-to-treatment failure, no imputation for missing data will be performed.

15.2.3.2. Missing Data Imputation Methods for Other Secondary Efficacy Endpoints

The primary analysis of the other secondary efficacy endpoints will be performed based on the observed-case. That is, no missing data will be imputed.

Additionally, LOCF will be used to impute missing data of endpoints based on CS7DA4S and SNOT-22 for sensitivity analyses. Multiple imputation will also be performed for endpoints based on CS7DA4A as sensitivity analysis, but not for the endpoints based on SNOT-22. No sensitivity analyses to the missing data imputation method will be performed for any other non-key secondary efficacy endpoint.

15.2.4. ANALYSIS OF KEY AND OTHER SECONDARY EFFICACY ENDPOINTS

15.2.4.1. Analysis of CFBL in CS7DA4S Individual and Total Scores at Weeks 8, 12, 16, 20 and 24

The analysis of the CFBL in CS7DAS total score will be conducted using an ANCOVA model as per Section 15.1.3. Week 24 is considered a key secondary endpoint, while Weeks 8, 12, 16, and 20 are considered as non-key secondary endpoints and all other visits as exploratory endpoints.

Additionally, the 7-day average score of nasal blockage/obstruction/congestion, reduction/loss of sense of smell, facial pain/pressure and anterior/posterior nasal discharge at Weeks 1, 2, 3, 4, 8, 12, 16, 20, 24 will be analyzed as per Section 15.1.3.

This analysis will be repeated for the ITT and PP analysis sets.

The same three sensitivity and supportive subgroup analyses as for the primary endpoint as detailed in Sections 15.1.4 and 15.1.5.2 will be repeated for the CS7DA4S total scores at all Weeks. Furthermore, the analysis of the CS7DA4S total score at all Weeks by CSsNP and CSwNP subgroups will be repeated with missing data imputed as per Section 15.1.2.

For all other endpoints, the sensitivity analyses based on the PP analysis set and based on the ITT analysis set but with missing data imputed based on LOCF will be performed. That is, no sensitivity analysis based on the ITT analysis set with missing data imputed based on the multiple imputation method will be performed for the other secondary efficacy endpoints.

Additionally, a plot of the LS means and SE for CFBL for CS7DA4S total and individual symptom scores at each timepoint up to Week 24 and Week 48 will be provided for the primary and final data analysis, respectively.

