### **10.6.4 Exploratory Endpoint Analysis**

A one-sided 0.05 level of significance will be used to compare treatments for each exploratory efficacy endpoint at each visit; there will be no adjustment for multiple comparisons. These analyses will be performed in the ITT analysis set with available data and repeated using subjects in the PP analysis set. There will be no imputation of missing data for these analyses.

The exploratory efficacy endpoints that are continuous variables will be compared between treatments at each post-Baseline time point in the same manner as the primary endpoint. For dichotomous efficacy endpoints, treatments will be compared using logistic regression adjusting for baseline score and randomization strata.

As further exploratory analyses on all endpoints measured longitudinally at various visits during the study, generalized estimating equation (GEE) linear regression (for continuous outcomes) and GEE logistic regression (for dichotomous outcomes) will be used to compare treatments over time; the assumed within-subject correlation matrix structure will be unstructured; if the unstructured model does not converge, then an autoregressive (1) structure will be assumed. Included as independent variables for each outcome variable will be treatment group, visit, treatment-by-visit and the baseline value of the variable being analyzed. If the treatment-by-visit interaction is not significant at the 0.10 level of significance, it will be removed from the GEE model. This will be carried out on ITT subjects with available data.

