7.3. MISSING DATA

Missing efficacy data for the primary and secondary endpoints will be handled as described in Sections 15.1.2 and 15.2.3, respectively. No missing data methods will apply for exploratory endpoints.

Missing safety data will not be imputed.

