15.1.2. MISSING DATA IMPUTATION METHODS FOR PRIMARY EFFICACY ENDPOINT

The primary analysis will not include any missing data imputation methods. The primary analysis of the primary efficacy endpoint will include subjects in the ITT analysis set with available CS7DA4S data at Baseline and Week 4 visit.

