15.2.4.5. Analysis of SNOT-22 and SF-36v2 Domain and Total Scores

For each post-Day 1 visit, the questionnaires will be compared between treatments using an ANCOVA model as described for the primary endpoint in Section 15.1.3 for the ITT analysis set. The CS7DA4S baseline score in

Section 15.1.3 will be replaced by the baseline score for the domain/total score of interest in the ANCOVA model. The summary of SNOT-22 will include the proportion of subjects who have achieved a minimally clinically important difference.

Additionally, a plot of the biweekly LS means and SE for CFBL for SNOT-22 total score over time up to Week 24 and Week 48 by treatment group will be provided for the primary and final data analyses, respectively.

The analysis for SNOT-22 will be repeated for the PP analysis set. In addition, analysis for SNOT-22 in the ITT analysis set will be repeated where missing data will be imputed using the LOCF method outlined in Section 15.1.4.

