15.3.2. MISSING DATA IMPUTATION METHODS FOR EXPLORATORY EFFICACY ENDPOINTS

No missing data methods will be used for exploratory analysis.

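### SAP 15.2.4.1 and 15.2.4.5 order imputation at visits that SAP 7.3 and 15.3.2 bar from imputation; on the wide reading, on-depot scores would fill post-removal visits in the durability sensitivity analyses

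*SAP*

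**What the plan says.** **The prohibition.** SAP 7.3: "No missing data methods will apply for exploratory endpoints". SAP 15.3.2: "No missing data methods will be used for exploratory analysis". Protocol 10.6.4, on the exploratory endpoints: "There will be no imputation of missing data for these analyses". SAP 3.3, which lists departures from the protocol, names none from this rule.

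**The contrary instructions.** SAP 15.2.4.1 makes Week 24 a key secondary visit for the CS7DA4S total and then says: "Weeks 8, 12, 16, and 20 are considered as non-key secondary endpoints and all other visits as exploratory endpoints". It goes on to order that the three sensitivity analyses of SAP 15.1.4 (per-protocol set, LOCF and MI), together with the subgroup analyses, "will be repeated for the CS7DA4S total scores at all Weeks". SAP 15.2.4.5 compares the questionnaires at every visit after Day 1 and adds: "analysis for SNOT-22 in the ITT analysis set will be repeated where missing data will be imputed using the LOCF method". Both sections call for plots that run to Week 48 at the final analysis. SAP 15.3.1.4 lists CS7DA4S and SNOT-22 at Weeks 28, 32, 36, 40, 44 and 48 as exploratory and has the secondary analysis repeated there.

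**The polyp subgroups.** SAP 15.2.4.1 also says that the CS7DA4S analysis in the CSsNP and CSwNP subgroups "will be repeated with missing data imputed as per Section 15.1.2". SAP 15.1.2 reads: "The primary analysis will not include any missing data imputation methods".

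**The concern.** Depots are removed at Week 24/EOT or earlier (protocol 6.5). Weeks 28-48 exist to show whether benefit lasts after removal. If a missing score at those visits is filled with the last score recorded while the depot was in place, an effect that has faded looks as if it has lasted.

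Timing adds to this. Under SAP 4.2, project teams are unblinded at the primary analysis, once all subjects have passed Week 28. The CS7DA4S and SNOT-22 results for the later post-treatment visits come at the final analysis (SAP 4.3). If the conflict is still open then, people who have seen treatment results could decide whether an imputed table for those visits is produced.

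The polyp-subgroup sentence is a separate fault. As written, it orders an imputed analysis and points to a section that contains no imputation method.

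**Working it through.** **Step 1: set the instructions side by side.**

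| Endpoint and visits | Status | Imputation ordered in | Barred by 7.3 / 15.3.2? |
|---|---|---|---|
| CS7DA4S total, Week 4 | primary | 15.1.4 | no |
| CS7DA4S total, Weeks 8-20 | non-key secondary | 15.2.3.2, 15.2.4.1 | no |
| CS7DA4S total, Week 24 | key secondary | 15.2.3.1, 15.2.4.1 | no |
| CS7DA4S total, Weeks 1-3 | exploratory (15.2.4.1) | 15.2.4.1, all-weeks wording | yes |
| CS7DA4S total, Weeks 28-48 | exploratory (15.2.4.1, 15.3.1.4) | 15.2.4.1, all-weeks wording | yes |
| SNOT-22, Weeks 2-24 | secondary (15.2.2.3) | 15.2.3.2, 15.2.4.5 | no |
| SNOT-22, Weeks 28-48 | exploratory (15.3.1.4) | 15.2.4.5, no week limit | yes |
| CS7DA4S by CSsNP / CSwNP | exploratory (15.3.1.3) | 15.2.4.1, via 15.1.2 | yes, and 15.1.2 has no method |

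Six post-treatment visits are affected for the CS7DA4S total, and the same six for SNOT-22. If the all-weeks wording stops at Week 24, Weeks 1-3 still conflict. The polyp-subgroup conflict does not depend on which weeks are meant.

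**Step 2: what LOCF would do after removal.** SAP 15.1.4 writes the rule for a missing Week 4 score: use the last available post-baseline score. It contains no stop at removal. Extended to Week 48, it has two cases:

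- A subject with a usable Week 28 score and nothing later carries the Week 28 score, which is post-removal.
- A subject with no usable score after removal carries a Week 24 or earlier score, which is on-depot in the active arms.

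Only the second case creates the bias. MI does not carry scores forward, and 15.2.4.5 uses LOCF only.

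**Step 3: check the planning inputs.** SAP 7.1 gives means of -1.30 (sham) and -3.00 (LYR-210), so the difference is -3.00 - (-1.30) = -1.70. The SD is 2.4, with 21 evaluable per group at one-sided 0.05. A noncentral t calculation for one dose against sham (40 df) gives 73.0%, matching the stated 73%. The power figure is not in dispute.

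**Step 4: size of the bias.** Let f be the share in each arm with no usable post-removal score. Assume that the on-depot difference is -1.70 and the true post-removal difference is 0. Then:

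spurious difference = f x (-1.70)

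The documents give no missing rate for Weeks 28-48. The nearest figure is the allowance of 6-9 extra subjects on 63:

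- 6/69 = 8.7%: 0.087 x (-1.70) = -0.15
- 9/72 = 12.5%: 0.125 x (-1.70) = -0.21

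With n = 23-24 per arm (69/3 and 72/3), the standard error is the square root of [(2.4² + f(1 - f) x 1.70²)/n + 2.4²/n]. At n = 23 this is about 0.71 for f = 8.7% and 0.72 for f = 12.5%. By normal approximation, the nominal one-sided 5% rejection rate for one dose rises to about 7.5% and 9%.

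The documents state no planning difference for SNOT-22, so no size is given for it.

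**The case against.** The strongest reply is that the plan, read in context, already excludes post-treatment imputation. The heading of 15.2.4.1 names only Weeks 8-24. SAP 15.2.2.3 derives the secondary SNOT-22 changes for Weeks 2-24. The imputation instruction in 15.2.3.2 sits under secondary endpoints. Weeks 28-48 have their own section, followed directly by the prohibition. The LOCF algorithm is written only for Week 4 and the MI algorithm only for Weeks 1-4, so no written rule actually carries a score past removal. The table shells (SAP 8) may settle which weeks get an imputed table, but they are not in the text available here.

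The narrow reading is therefore possible, but the text does not settle on it. The body of 15.2.4.1 reaches beyond its heading to all other visits, both sections plot to Week 48, and 15.3.1.4 repeats the secondary analysis after treatment. The polyp-subgroup fault survives every reading.

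Three objections to the size of the harm stand:

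- The imputed runs are sensitivity analyses. The main analysis is observed-case, and all p-values are nominal (SAP 7.8).
- Applying -1.70 to everyone missing at a visit overstates the bias, because subjects with any post-removal score carry that score.
- The -1.70 is a Week 4 planning value, and the bias at the plan's own allowance is small against a standard error near 0.71.

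**Conclusion.** The contradiction is real and should be resolved in the text. It concerns sensitivity analyses of exploratory visits and subgroups, and leaves the primary and key secondary analyses untouched. On the wide reading, LOCF biases the durability sensitivity analyses toward lasting benefit. The illustrative upper bound is about -0.15 to -0.21 CS7DA4S points. It assumes that the whole dropout allowance has no post-removal score, equally in each arm, that the planning difference holds on depot, and that it is fully lost after removal. Partial loss of effect, or fewer such subjects, makes the bias smaller.

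A reader might infer more, and the documents do not support it:

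- **That the durability conclusion itself is biased.** The main analysis of those visits uses observed data.
- **That the bias reaches -0.34 or -0.51 points.** Those values need 20% or 30% of subjects with no post-removal score, which exceeds the plan's allowance and has no source in the documents.
- **That MI has the same fault.** It would predict post-removal scores from earlier ones, but it does not carry them forward.
- **That an analyst may freely choose between two results.** The observed-case analysis is designated, and an imputed one would be an added output.

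**What to change.** 1. In SAP 15.2.4.1, replace the all-weeks wording for LOCF and MI with Weeks 8, 12, 16, 20 and 24. Week 4 is already covered by 15.1.4. If Weeks 1-3 are also to be imputed, exempt them explicitly in 7.3 and 15.3.2.
2. In SAP 15.2.4.5, limit SNOT-22 LOCF to Weeks 2-24.
3. State that Weeks 28-48 are analysed as observed and that no treatment-stage score fills a post-treatment visit. Do not phrase this as a general ban on carrying scores across the removal date. That would block the Week 24 LOCF that protocol 10.6.2.1 and SAP 15.2.3.1 specify, for subjects whose depots came out early and who lack a Week 24 score.
4. Delete the imputed CSsNP/CSwNP sentence, or point it to 15.1.4 and exempt it from 7.3 and 15.3.2.

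The cost is SAP wording and slightly fewer outputs. No data collection changes. The edits should be made before unblinding for the primary analysis.

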15.2.4.2. Analysis of Zinreich Score

The number and percentage of subjects at Week 24 in the ITT analysis set with and without at least a 1-point decrease in one of the six bilateral Zinreich sinuses score as defined in Section 15.2.1.2 will be provided by treatment group.

A logistic regression adjusting for the baseline total bilateral Zinreich score and stratification variables (nasal allergy and nasal polyps) will be used to compare treatment groups. The responder indicator will be set to 1 for subjects who achieve at least a 1-point decrease in any score at Week 24 compared to baseline. Subjects for whom the decrease cannot be calculated, for example due to early termination, will be excluded from the analysis.

Odds ratios together with the 90% CI will be presented to compare treatment groups. This analysis will be repeated for the PP analysis set.

As non-key secondary analyses, the CFBL in each of the 5 bilateral Zinreich sinuses score, Zinreich OMC score and total Zinreich score at Week 24 will be analyzed using an ANCOVA model as specified in Section 15.1.3 replacing the baseline CS7DA4S with the appropriate baseline bilateral Zinreich sinuses score, Zinreich OMC score or baseline Zinreich total score. This analysis will be repeated for the PP analysis set.

Additionally, the logistic regression and ANCOVA models will be repeated on the subgroups as per baseline median total bilateral Zinreich score, for the ITT analysis set.

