
To assess efficacy of LYR-210 in improving CS7DA4S score, the 7-day average score of each of 4 CS cardinal symptoms, the SNOT-22 total and subdomain scores, and the SF-36v2 physical health, mental health, and domain scores in the subgroups of CS subjects without nasal polyps (CSsNP) and CSwNP subjects
	
 
- CFBL in the CS7DA4S score at Weeks 1, 2, 3, 4, 8, 12, 16, 20, and 24
 
- CFBL in 7-day average score of nasal blockage/obstruction/congestion, reduction/loss of sense of smell, facial pain/pressure, anterior/posterior nasal discharge in CSsNP and CSwNP subjects at Weeks 1, 2, 3, 4, 8, 12, 16, 20, and 24
 
- CFBL in total SNOT-22 score and SNOT-22 rhinologic, extra-nasal rhinologic, ear-facial, sleep dysfunction, and psychological subdomain scores in CSsNP and CSwNP subjects at Weeks 2, 4, 8, 12, 16, 20, and 24
 
- CFBL in SF-36v2 physical health, mental health, and each of the health domain scores in CSsNP and CSwNP subjects at Week 24
 

To assess efficacy of LYR-210 in reducing sinus inflammation in CSsNP and CSwNP subjects
	
 
- Percentage of subjects with at least 1-point decrease in the bilateral Zinreich score in at least 1 pair of the anterior ethmoid, maxillary, posterior ethmoid, frontal, or sphenoid sinuses in CSsNP and CSwNP subjects at Week 24
 
- CFBL in bilateral Zinreich scores of posterior ethmoid, frontal, sphenoid, maxillary, anterior ethmoid sinus, and OMC pairs in CSsNP and CSwNP subjects at Week 24
 
- CFBL in total Zinreich score at in CSsNP and CSwNP subjects at Week 24
 

To assess effect of LYR-210 in improving smell function in CSsNP and CSwNP subjects
	
 
- CFBL in UPSIT score in CSsNP and CSwNP subjects at Week 24
 

To assess the safety of subjects post LYR-210 treatment
	
 
- Severity and percentage of subjects reporting AEs and SAEs through Week 28 and Week 48
 
- Percentage of subjects with abnormal and clinically significant abnormal laboratory values (hematology and chemistry, vital signs) at Week 28
 
- Morning serum cortisol levels at Week 28
 
- Plasma MF concentrations at Week 28
 

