
To assess effect of LYR-210 in reducing polyp severity within middle meatus in subgroup of CS subjects with nasal polyps (CSwNP)
	
 
- Percentage of subjects with improvement from Baseline in nasal polyp severity within middle meatus in CSwNP subjects at Week 24
 

To assess efficacy of LYR-210 in improving CS7DA4S score, the 7-day average score of each of 4 CS cardinal symptoms, the SNOT-22 total and subdomain scores, and the SF-36v2 physical health, mental health, and domain scores in the subgroups of CS subjects without nasal polyps (CSsNP) and CSwNP subjects
	
 
- CFBL in the CS7DA4S score at Weeks 1, 2, 3, 4, 8, 12, 16, 20, and 24
 
- CFBL in 7-day average score of nasal blockage/obstruction/congestion, reduction/loss of sense of smell, facial pain/pressure, anterior/posterior nasal discharge in CSsNP and CSwNP subjects at Weeks 1, 2, 3, 4, 8, 12, 16, 20, and 24
 
- CFBL in total SNOT-22 score and SNOT-22 rhinologic, extra-nasal rhinologic, ear-facial, sleep dysfunction, and psychological subdomain scores in CSsNP and CSwNP subjects at Weeks 2, 4, 8, 12, 16, 20, and 24
 
- CFBL in SF-36v2 physical health, mental health, and each of the health domain scores in CSsNP and CSwNP subjects at Week 24
 

To assess efficacy of LYR-210 in reducing sinus inflammation in CSsNP and CSwNP subjects
	
 
- Percentage of subjects with at least 1 point of decrease in the bilateral Zinreich score in at least 1 pair of the posterior ethmoid, frontal, or sphenoid sinuses in CSsNP and CSwNP subjects at Week 24
 

	
 
- CFBL in bilateral Zinreich scores of posterior ethmoid, frontal, sphenoid, maxillary, anterior ethmoid sinus, and OMC pairs in CSsNP and CSwNP subjects at Week 24
 
- CFBL in total Zinreich score at in CSsNP and CSwNP subjects Week 24
 

To assess effect of LYR-210 in improving smell function in CSsNP and CSwNP subjects	
 
- CFBL in UPSIT score in CSsNP and CSwNP subjects at Week 24
 

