#### **10.6.2 Key Secondary Efficacy Endpoint Analysis**

The key secondary endpoints are:

- CFBL in CS7DA4S score at Week 24
- Percentage of subjects with at least 1-point decrease in bilateral Zinreich score in at least one pair of the anterior ethmoid, maxillary, posterior ethmoid, frontal, or sphenoid sinuses at Week 24
- Time to treatment failure: A treatment failure is defined as, after subject enrollment, the subject being recommended by treating physician for oral corticosteroid or ESS due to worsening of CS symptoms, or the subject complaint of persistent CS symptoms with an average CS7DA4S score over the preceding 30 days greater than or equal to the Baseline CS7DA4S score.

For each key secondary endpoint, each LYR-210 dose will be compared to sham at a one-sided 0.05 level of significance. There will be no adjustment of the significance level for multiple comparisons across the secondary endpoints.

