15.2. SECONDARY EFFICACY

15.2.1. KEY SECONDARY EFFICACY ENDPOINTS AND DERIVATION

15.2.1.1. CFBL in CS7DA4S at Week 24

CFBL at Week 24 will be derived as described in Section 15.1.1.

15.2.1.2. Proportion of Subjects with at Least 1-point Decrease in Bilateral Zinreich Score in at Least One Pair of Anterior Ethmoid, Maxillary, Posterior Ethmoid, Frontal or Sphenoid Sinuses at Week 24

Sinus inflammation will be assessed by MRI at time points specified in the schedule of events in Section 8.1 of the protocol. The sinus inflammation will be assessed using the Zinreich modified Lund-Mackay scoring system (Likness, et al., 2014). The Zinreich score for each sinus will be assessed by Medical Metrics, Inc. (MMI) and all analysis will use the data collected by MMI. Six areas of each sinus (left and right) will be assessed:

- Anterior ethmoid
- Maxillary
- Posterior Ethmoid
- Frontal
- Sphenoid
- Ostiomeatal Complex (OMC)

Each area will be assigned a score based on the percentage of opacification as follows:

- 0=0%
- 1=1%-25%
- 2=26%-50%
- 3=51% to 75%
- 4=76% to 99%
- 5=100% or completely occluded

The OMC is given a score of 0 to 2 as follows:

- 0=completely patent
- 1=partially occluded
- 2=completely occluded

The bilateral Zinreich score for each area will be derived by [REDACTED] Biostatistics by adding the score for both sinuses together. The range of the score will be 0-10 except for OMC which will have a range of 0-4. The bilateral Zinreich score for each area will only be calculated if both sinus scores are non-missing. The total bilateral score

will be the sum of all 6 areas and will have a range of 0-54. The total bilateral score will only be calculated when all bilateral scores for each of the 6 areas are present. The baseline bilateral Zinreich score for each area and baseline total score will be the value recorded at screening. The individual and total Zinreich scores for all areas at all visits will be summarized and listed.

The key secondary endpoint will be the proportion of subjects with at least 1-point decrease from baseline in the Zinreich score in at least 1 pair of the anterior ethmoid, maxillary, posterior ethmoid, frontal or sphenoid sinuses at Week 24.

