15.3.1.3. CFBL in Endpoints by Absence or Presence of Nasal Polyps

The secondary endpoints analysis will be repeated using the subgroups of subjects without nasal polyps (CSsNP), and subjects with nasal polyps (CSwNP). The endpoints to be summarized by these subgroups are:

- CFBL in CS7DA4S score at Weeks 1, 2, 3, 4, 8, 12, 16, 20 and 24

- CFBL in 7-day average score of individual cardinal CS symptoms at Weeks 1, 2, 3, 4, 8, 12, 16, 20 and 24
- CFBL in SNOT-22 domain and total scores at Weeks 2, 4, 8, 12, 16, 20 and 24
- CFBL in SF-36 domain and overall component summary measure scores at Week 24
- Percentage of subjects with at least 1-point decrease in any area for the bilateral Zinreich score at Week 24
- CFBL in each of the 5 bilateral Zinreich sinus scores, Zinreich OMC score and Zinreich total score at Week 24
- CFBL in USPIT™ total olfaction score at Week 24

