15.3.3. ANALYSIS OF EXPLORATORY EFFICACY ENDPOINTS

The exploratory efficacy endpoints that are continuous will be compared between treatments at each post-baseline timepoint in the same manner as the primary efficacy analysis in Section 15.1.3 for the ITT analysis set. For the efficacy endpoints to be analyzed by CSsNP and CSwNP subgroups, the analysis will be a repeat of Section 15.1.3, however the model will not include the presence of nasal polyps as a fixed effect.

For dichotomous exploratory efficacy endpoints, treatments will be compared in the same manner as the proportion

of subjects with at least 1-point decrease from baseline in the Zinreich score in at least 1 pair of the anterior ethmoid, maxillary, posterior ethmoid, frontal or sphenoid sinuses key secondary endpoint in Section 15.2.4.2, replacing the baseline bilateral Zinreich score with the baseline CS7DA4S score. This analysis will be carried out for the ITT analysis set.

In addition, for all endpoints measured longitudinally at various visits during the study, a generalized estimating equation (GEE) linear regression and logistic regression will be used to compare treatments over time for continuous and dichotomous endpoints, respectively. The estimates, SE, 90% CIs and p-values will be presented for each visit. In the GEE, only treatment stage timepoints will be analyzed; assessments with only one follow-up timepoint will not be analyzed.

The assumed within-subject correlation matrix structure will be unstructured. If the unstructured model does not converge, then an autoregressive (1) structure will be assumed. Included as independent variables for each outcome endpoint will be treatment group, visit, treatment-by-visit, stratification variables, and the baseline value of the endpoint being analyzed. This will be carried out on ITT subjects with available data for the below endpoints:

- CFBL in CS7DA4S total score
- CFBL in 7-day average score of individual cardinal CS symptoms
- CFBL in SNOT-22 domain and total scores

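### The SAP codes the Zinreich responder on six areas, ostiomeatal complex included, although the key secondary endpoint is defined on five sinus pairs

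*SAP*

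**What the plan says.** **Definition.** Protocol 10.6.2 places the required fall "in at least one pair of the anterior ethmoid, maxillary, posterior ethmoid, frontal, or sphenoid sinuses at Week 24". The Synopsis, Section 3 and Section 10.6.2.2 name the same five pairs. The endpoint sentence that closes SAP 15.2.1.2 also requires it "in at least 1 pair of the anterior ethmoid, maxillary, posterior ethmoid, frontal or sphenoid sinuses at Week 24". When SAP 15.3.3 refers back to this analysis it again describes the five-pair endpoint, ending "maxillary, posterior ethmoid, frontal or sphenoid sinuses key secondary endpoint in Section 15.2.4.2". None of these places includes the OMC.

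**Analysis.** SAP 15.2.4.2 first asks for the number and percentage of subjects with a "1-point decrease in one of the six bilateral Zinreich sinuses score as defined in Section 15.2.1.2". Its next paragraph, on the logistic regression, states: "The responder indicator will be set to 1 for subjects who achieve at least a 1-point decrease in any score at Week 24". Neither sentence excludes the OMC.

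**Polyp subgroups.** The exploratory version of this responder appears in three forms:
- SAP 15.3.1.3: "Percentage of subjects with at least 1-point decrease in any area for the bilateral Zinreich score at Week 24".
- Protocol Synopsis: "in at least 1 pair of the anterior ethmoid, maxillary, posterior ethmoid, frontal, or sphenoid sinuses in CSsNP and CSwNP subjects at Week 24".
- Protocol Section 3: "in at least 1 pair of the posterior ethmoid, frontal, or sphenoid sinuses in CSsNP and CSwNP subjects at Week 24", which is three pairs.

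**The concern.** The section that defines the endpoint and the section that programs it do not describe the same responder. Two competent programmers could produce different responder counts, and so different odds ratios and p-values, for a key secondary endpoint. The literal coding rule is also an undeclared departure from the pre-specified definition: SAP 3.3 lists the changes from the protocol, down to mean versus median imputation of questionnaire items, and does not mention adding the OMC. If the choice between five and six is made after unblinding, either answer can look data-driven.

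**Working it through.** **1. Which area is the sixth?** SAP 15.2.1.2 lists six scored areas, the OMC last. Each sinus pair is scored 0 to 10 and the OMC pair 0 to 4. Then 5 × 10 + 4 = 54, the stated maximum of the total. The six scores are therefore the five sinus pairs plus the OMC.

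**2. Does a fall in any score go beyond the six areas?** No. The total is the sum of the six area scores, so it cannot fall unless at least one area falls. The two rules differ only in subjects whose sole improvement is in the OMC. The six-area rule can keep or raise each arm's responder rate; it cannot lower it.

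**3. Does the cross-reference settle it?** No. SAP 15.2.1.2 contains both the six-area list and the five-pair endpoint, so pointing to it supports either reading. The sentence that defines the regression indicator carries no cross-reference.

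**4. How many subjects could change status?** There is no figure in the plan to reproduce: the documents give no expected response rate for this endpoint. Every rate below is an assumption. Let q be the chance of a fall in each sinus pair and o the chance of a fall in the OMC. Under independence:

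- any of five = 1 − (1 − q)^5
- any of six = 1 − (1 − q)^5 × (1 − o)
- extra responders per 21 subjects = 21 × (1 − q)^5 × o

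The 21 is the evaluable number per arm in SAP 7.1, which was set for the primary endpoint.

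| q | Any of five | Any of six, o = q | Extra per 21, o = q | Extra per 21, o = q/2 |
|---|---|---|---|---|
| 0.1 | 41.0% | 46.9% | 1.24 | 0.62 |
| 0.2 | 67.2% | 73.8% | 1.38 | 0.69 |
| 0.3 | 83.2% | 88.2% | 1.06 | 0.53 |

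Falls in neighboring areas are likely to be correlated. A one-factor Gaussian model with common correlation ρ gives these extra responders per 21:

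| ρ | o = q (q = 0.1 / 0.2 / 0.3) | o = q/2 (q = 0.1 / 0.2 / 0.3) |
|---|---|---|
| 0.3 | 0.82 / 0.96 / 0.88 | 0.36 / 0.39 / 0.33 |
| 0.5 | 0.60 / 0.73 / 0.72 | 0.22 / 0.24 / 0.20 |
| 0.7 | 0.39 / 0.51 / 0.53 | 0.11 / 0.11 / 0.09 |

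Across this grid the excess is about 0.1 to 1.4 per 21. One reclassified subject moves an arm's rate by 1/21 = 4.8 percentage points.

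**5. Which way could the contrast move?** Assume independence, q = 0.2 on sham and q = 0.3 on active.

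| Rule | Sham | Active | Difference |
|---|---|---|---|
| Five pairs | 67.2% | 83.2% | 16.0 points |
| Six areas, o = 0.2 in both arms | 73.8% | 86.6% | 12.8 points |
| Six areas, o = 0.1 sham, 0.4 active | 70.5% | 89.9% | 19.4 points |

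The direction depends on how OMC-only falls split between the arms, which the documents do not tell us.

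**The case against.** The strongest reply is that this is a one-word slip and that the documents already point to five pairs. The heading and the closing sentence of SAP 15.2.1.2 name them, SAP 15.3.3 names them when describing this very analysis, and the protocol agrees throughout. SAP 15.2.4.2 itself later separates five sinus scores from the OMC score. The sentence with the word six governs only a descriptive table, and the indicator sentence can be read as shorthand for the endpoint just cited.

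Much of this stands as evidence of intent: five pairs is very probably what was meant. It does not rescue the text. Because the same section distinguishes five from the OMC when it wants to, six cannot simply be read as five, and the indicator sentence is open-ended.

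The reply is also right about magnitude. The 0.1 to 1.4 range belongs to the chosen grid, not to every plausible case. With q = 0.5 the excess under independence is 0.16 to 0.33 per 21 (o = q/2 to o = q). With q = 0.7 it is 0.01 to 0.25 across the same correlations, so when most subjects respond the conflict nearly vanishes.

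The three-pair versus five-pair conflict in the protocol is a separate matter in an exploratory endpoint. It adds no weight to the main point, but the same edit should settle it. Finally, the output shells mentioned in SAP 8 are not in the documents and may already be correct.

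**Conclusion.** The concern holds. SAP 15.2.4.2, followed literally, gives a responder count that departs from the key secondary endpoint as defined in the protocol and in SAP 15.2.1.2, and the departure is not declared. That rests on the text alone. Which version would be programmed cannot be told from the documents, so the right statement is that OMC-only falls could be counted.

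The size is probably small, in most of the assumed scenarios less than one subject per arm, and its effect on the comparison with sham is of unknown sign. The primary endpoint is not affected, and SAP 7.8 makes all p-values nominal. It should be fixed, but it does not threaten the trial's main conclusion.

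**What to change.** - **SAP 15.2.4.2:** in both the table sentence and the indicator sentence, replace the six-area and any-score wording with at least one of the five bilateral sinus-pair scores (anterior ethmoid, maxillary, posterior ethmoid, frontal, sphenoid), excluding the OMC.
- **SAP 15.3.1.3:** align the any-area wording to the same five pairs.
- **SAP 3.3:** record which version of the polyp-subgroup responder applies, given three pairs in protocol Section 3 and five in the Synopsis. If the sponsor did intend to include the OMC in the key secondary endpoint, it must be declared here as a change from the protocol.
- **Output shells:** check that they match.

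All of this should be done before unblinding for the primary data analysis. The cost is a few words in two SAP sections, one entry in SAP 3.3 and a check of the shells. No new data are needed and the primary analysis does not change.
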